PROTOCOL TITLE: *Use of simulation to improve ventricular assist device self-management: A Quantitative Study*

PRINCIPAL INVESTIGATOR:

*[name]
Department of Hospital Medicine and Medical Education
[contact]
[contact]*

VERSION NUMBER:

2

VERSION DATE:

7/3/17

OBJECTIVES:

AIM 1. Compare performance of VAD self-management skill of sterile dressing changes and VAD-related controller functions, between SBML-trained and the usual VAD training group immediately following training, and at one and three months after VAD implantation.

Hypothesis 1a: VAD patients and their caregivers will demonstrate better VAD self-management skills when trained with the SBML intervention compared to the usual VAD training group.

Hypothesis 1b: VAD patients and their caregivers will demonstrate better VAD self-management skill retention at one and three months compared to the usual VAD training group.

AIM 2. This exploratory aim will examine VAD-patient driveline infections, and all-cause and infection-related re-hospitalizations through one and three months after VAD implant, between the SBML intervention group as compared to the usual VAD training group.

Hypothesis: Patients who complete the SBML VAD curriculum with their caregivers will have lower infections and re-hospitalizations compared to the usual VAD training group.

BACKGROUND:

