Each individual enrolled will participate in the study for approximately 3 months. We anticipate enrollment of study subjects will take approximately 15 months. We hope to complete all analyses 2 two years.

STUDY ENDPOINTS:

The primary study endpoints are we have enough patients enrolled to compare VAD-care SBML training and usual training groups.

PROCEDURES INVOLVED:

Approximately 60 advanced HF patients undergo VAD implantation at NMH yearly. During our 15-month study period, up to 75 participating patients and 75 caregivers will be eligible to receive either the SBML VAD self-management curriculum or usual VAD training. Eligible patients will be about to undergo VAD implantation at NMH, age >18, and English-speaking. Eligible caregivers will be identified by a VAD implantation patient, age >18, and English-speaking. Advanced HF patients who are scheduled for VAD implantation will receive information about the study at their pre-implantation clinic visits or during hospitalization. Consenting patients will be asked to provide the name and contact information of their primary caregiver; we will contact the caregivers to explain the study and assess their interest. Patients and caregivers must both agree to participate in the study to be enrolled. All Patient and caregiver VAD self-management training begins before implantation and continues up to the hospitalization for VAD placement.

Study randomization will be conducted via random number generator. After randomization, demographic data including age, sex, race/ethnicity, and socioeconomic (SES) factors such as zip code, highest level of education, and employment status will be collected from patients and caregivers.

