then will participate in deliberate practice on the simulator with feedback from the instructor. We anticipate 2 training sessions of 1-2 hours each to become proficient in these skills. After training, the patient and caregiver complete a post-intervention assessment on the simulator using the checklists. At the end of training, the patient and caregiver will complete the written examination to assess knowledge and will be required to meet or exceed the MPS on the checklists and written examination. If they fail to meet the MPS, they will receive additional training until they meet the MPS. If the patient is ever too ill, only the caregiver will participate in the training and the patient will be trained during the hospital stay for implantation. Both training groups. After training, we will ask participants to rate their educational experience and their confidence in performing each of the 5 VAD self-management tasks [via a questionnaire adapted from our previous work. All participants will demonstrate the five skill domains on the actual VAD patient during the implantation hospitalization (Time 0), and at one and three months after training to assess skill retention. Assessments will be performed during office visits, as patients are seen at least monthly after VAD implantation, or re-hospitalizations. If caregivers cannot attend, assessments will be performed via internet video. We anticipate the majority of enrolled patients will have internet access; alternatively, we will arrange sessions at their local library.

A trained VAD nurse (who is not assigned to teach the curriculum) will perform all patient and caregiver assessments using the checklist. In the absence of this nurse, the PI or a Co-I will perform assessments; we expect this to be rare. The trained VAD nurse, the PI and COCo-I will be blind to the intervention received by the patient and caregiver. A random sample of 25% of all assessments will be double scored by both the VAD nurse and PI or Co-I to assess inter-rater reliability.

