We will estimate checklist score inter-rater reliability using the Kappa (κ) coefficient^{84,87}. Our prior work shows the difference between traditional training and SBML interventions is approximately 33%; traditionally trained simulated skill checklist performance averages 61.47% (SD=24.48) items correct while SBML training performance averages 94.88% (SD=6.63).^{9,48,51,53,88} We anticipate the usual training group in our study will perform similarly to the traditionally trained healthcare providers in our prior studies. Sample sizes of 65 in each group (total =130) achieve 82% power to detect at least 10% difference between the usual group and the SBML training group assuming a mean checklist score of 85% in usual group (SD=25) and 95% in the SBML training group (SD=10) with a significance level of 0.05 using a two-sided t-test. As the distribution of % items correct is likely to be non-parametric, adding 15% requires 75 in each group.⁸⁹ Therefore, our study will be overpowered to detect a 33% difference. We will compare checklist scores on actual patient assessments between usual care and SBML-trained groups using the independent t-test or Wilcoxon rank sum test (if data are non-parametric). We will compare age, sex, race/ethnicity, level of education, employment status, zip code, type of VAD, and VAD indication (DT vs. BTT) between groups using either Chi Square test or independent t-tests. If there is a difference between the randomized groups in any of these variables at the level of $p \leq 0.1$, we will use multiple linear regression or multiple quantile regression (for non-parametric data) to assess these variables independently on scores between the two groups. We will measure skills decay between groups using an analysis of variance (ANOVA) or a non-parametric analysis of variance at 0, 1 and 3-month assessments. Questionnaire results will be compared between groups using Chi-Square, independent t-test, or Wilcoxon rank sum where appropriate.

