We will compare driveline infections and re-hospitalization rates at one and three months after VAD implantation between the SBML and the usual training groups using the Chi Square test, recognizing that we may be underpowered for this exploratory aim due to the short study time frame. We will compare age, sex, race/ethnicity, level of education, employment status, zip code, type of VAD, VAD indication (DT vs. BTT), and Charlson scores between groups using either the Chi Square test or independent t-tests. If there is a difference between the randomized groups in any of these variables at the level of $p \leq 0.1$, we will perform multiple logistic regression to control for these independent variables between groups. If some patients have more than infection, we will use random effects modeling to account for clustering by patient.

The study PIs, co-investigators, as needed, VAD nurse, and Research Coordinator (RC) will have access to individually identifiable data. Otherwise, a unique identification code will be assigned to each enrolled patient, and all of the data entered into the system for that patient will be identified by this code rather than by name.

Socio-demographic and medical records data will be collected by INTERMACS and exported to a secure web server at Northwestern University. Socio-demographic data collected from VAD caregivers and checklist of VAD self-maintenance tasks-performance data will be collected on paper but will be de-identified using a unique identifier for each patient or caregiver. This data will be stored on a Northwestern Server that is password protected and encrypted. All data will be collected specifically for research purposes.

WITHDRAWAL OF PARTICIPANTS:

Participants are free to withdraw from the study at anytime without consequences.

RISKS TO PARTICIPANTS:

There are two potential risks of participating in this study for patients:

1. Potential for breach of patient confidentiality. This is a very serious potential risk to patients, but safety measures, as described above, have been put into place and are monitored by the Northwestern University IRB.

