2. The simulation training may be superior or inferior to usual care, which means patients assigned to either simulation or usual care groups may receive worse VAD related self-management care training. We will review data from our study every 3 months and if there are significant differences in complications between groups, we will either stop the study or provide a cross-over arm.

POTENTIAL BENEFITS TO PARTICIPANTS:

There may be no potential benefit to the individuals participating in this study if the intervention proves equipose with the usual care. However, the information gained from these results will inform healthcare providers how to better train patients and their caregivers in self-management techniques. Furthermore, if the intervention is successful, the benefit to patients and their caregivers could be improved knowledge of VAD self-management techniques and reduction in VAD-related complications.

SETTING:

Patients will be recruited either at the medical center (while the patient is hospitalized) or during a clinic visit. Training and assessments will take place in the patient room or in NMH conference rooms.

RESOURCES AVAILABLE:

[name], MS, Principal Investigator

[name] is a Clinical Associate Professor in the Department of Medicine and Medical Education at Northwestern University Feinberg School of Medicine. He also serves as the Director of Simulation and Patient Safety and Associate Program Director for the Internal Medicine Residency Program. He has extensive experience with the use of simulation for healthcare education. He has lectured at national and international conferences on curricula development and procedure skills training, and has assisted several institutions in setting up simulation-based training programs similar to those described in this grant application. Additionally, [name] has close to 50 peer-reviewed publications using simulation-based mastery learning for training physicians and has won international awards for his research which has been previously funded by Agency for Healthcare Research and Quality. As PI of this study, [name] will be responsible for study design and IRB approval, administrative oversight and training of research personnel, curriculum development, simulation training, data acquisition storage and analysis, and manuscript preparation.

[name], Co-Investigator

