The research settings for recruitment and enrollment of patients is Northwestern Memorial Hospital, Northwestern University, Chicago, IL. Patients will be recruited either at the medical center (while the patient is hospitalized) or during a clinic visit. The co-investigators, who provide care to patients with ventricular assist devices (VADs) will share information about the study with patients. If the patient's caregiver is not present at this time, we will contact them via phone or via mailed brochure to explain the study and then consent in person when they arrive for their VAD training.

The PI, CO-I or VAD nurse, will further explain the study to patients and caregivers, encourage them to ask questions, and obtain written informed consent. Patients and caregivers will be informed that if they decline to participate in the study, it will not prejudice current patient care, and they may discontinue participation at any time during the study with no adverse impact to their treatment or care. Verbal and written information provided to potential participants during informed consent will include the following: the purpose of the study, the nature of the questions asked during interviews, the method and frequency of skills assessment completion, the length of time required, the voluntary nature of participation in the study, the ability to not respond or participate in any parts if requested, the freedom to withdraw from the study at any time without consequences, the potential risks and benefits of study participation,

and the confidentiality of information gathered. A brochure with an overview of the study will also be provided. Patients will also be shown their study results, if desired. Patients who are enrolled in INTERMACS will also be informed that INTERMACS will securely transmit data to Northwestern, as well, which is already done for other studies. We will also incorporate language into their consent form that includes a statement about INTERMACS protected health information being transmitted securely to Northwestern. Patients who agree to participate in the study will sign an informed consent form. A copy of the signed consent form will be given to the patient, a second copy of the consent form will be placed in the patient's medical record, and the original copy will be kept and filed by the RC

NUMBER OF LOCAL PARTICIPANTS:

We expect to recruit 75 patients and 75 caregivers. One caregiver will be identified by each patient subject.

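### Does the three-monthly complication review need a formal stopping boundary before the plan can be relied on?

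*Combined protocol and SAP*

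**What the plan says.** The rule is the second item under RISKS TO PARTICIPANTS: "We will review data from our study every 3 months and if there are significant differences in complications between groups, we will either stop" or offer cross-over. It comes directly after the remark that either form of training might turn out to be the worse one.

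The elements of a formal rule appear elsewhere, but for other purposes:

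- **Complications.** BACKGROUND calls driveline infection a complication, and PROCEDURES INVOLVED says such infections are tracked with INTERMACS definitions. Aim 2 under OBJECTIVES adds "all-cause and infection-related re-hospitalizations through one and three months after VAD implant".
- **Test.** DATA AND SPECIMEN MANAGEMENT says "We will compare driveline infections and re-hospitalization rates at one and three months after VAD implantation" between the groups "using the Chi Square test, recognizing that we may be underpowered for this exploratory aim due to the short study time frame".
- **Level.** The only significance level for an outcome is in the checklist sample-size statement: "with a significance level of 0.05 using a two-sided t-test".
- **Number of looks.** STUDY TIMELINES says "We anticipate enrollment of study subjects will take approximately 15 months", and NUMBER OF LOCAL PARTICIPANTS says "We expect to recruit 75 patients and 75 caregivers".
- **Blinding.** PROCEDURES INVOLVED says "The trained VAD nurse, the PI and COCo-I will be blind to the intervention received by the patient and caregiver".

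None of these is tied to the three-monthly review. Part of the staff listing under RESOURCES AVAILABLE was not in the text available for this review, so what it may say about who reviews is unknown.

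**The concern.** The sentence commits the team to act, and the action is drastic. Stopping truncates Aim 1. Opening cross-over could remove the randomised contrast at one and three months. The trigger would be a difference in outcomes that the plan itself calls exploratory and possibly underpowered, examined about five times with no stated adjustment. If the word significant means p below 0.05 each time, chance alone could end the trial early more often than one test in twenty suggests.

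Two people could also apply the sentence to the same table and disagree. The test, its continuity correction, the endpoints and the patients counted are all left open.

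A second worry is who looks. The investigators who may see data by arm include people who must stay blind because they are back-up and second scorers of the checklists.

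**Working it through.** The plan states no error rate or boundary for this review, so there is no figure to reproduce. The question is how much the open choices matter.

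**Inputs from the plan.** 75 patients, 15 months of enrolment, a review every 3 months, and about 3 months of participation each. Reviews at months 3, 6, 9 and 12 could cut enrolment short. One at month 15 could affect only the remaining follow-up.

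**Assumptions.** 1:1 simple randomisation, even accrual, implantation at enrolment, events spread evenly over 3 months, equal event rates of 5% to 40% in both arms, and two-sided 0.05 at each look. The plan gives no complication rate and sets no level for this review.

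**Same data, different decision.** Take 4 infections against 0 with 30 patients per arm. The cross-product difference is 4 × 30 − 26 × 0 = 120.

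- Uncorrected chi-square: 60 × 120² / (30 × 30 × 4 × 56) = 864,000 / 201,600 = 4.29, p = 0.038.
- Continuity-corrected: 60 × (120 − 30)² / 201,600 = 486,000 / 201,600 = 2.41, p = 0.12.
- Fisher's exact test: p = 0.11.

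The expected count is only 2 infections per arm, where the uncorrected test is least trustworthy. An analyst would normally turn to the exact or corrected version.

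**False-trigger chance for one endpoint** (simulation, 40,000 replicates per cell; ranges cover event rates of 5% to 40% and counting either all enrolled patients or only those with 3 months completed):

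| Test | 4 looks | 5 looks | Single look, month 15 |
|---|---|---|---|
| Uncorrected | 3–15% | 5–17% | 3–5% |
| Continuity-corrected | 0.3–6% | 0.5–7% | 0.3–3% |

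I re-ran this table and it agreed within simulation error. The large-sample value for five equally informative looks is 14.2%. Fisher's exact test with 37 per arm and five looks gives 3.0% to 6.5% at event rates of 10% to 40%. That five looks exceed one is inevitable, because the single look is one of the five.

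If any of three complications could trigger (driveline infection, all-cause and infection-related re-hospitalization, with assumed joint rates), five looks give 17–30% uncorrected and 5–12% corrected. I did not re-run those figures.

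**Price of a stricter level** (five looks, all enrolled patients, uncorrected test):

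| Nominal level per look | False trigger, 30% in both arms | Detection of a true 20-point difference |
|---|---|---|
| 0.05 | 15% | 50–54% |
| 0.03 | 9% | 40–44% |
| 0.02 | 6% | 33–37% |
| 0.016 | 5% | 30–33% |
| 0.01 | 3% | 23–27% |

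Detection is for 20% v 40% or 30% v 50%. I re-ran this table too, and it agreed. At 0.016 the rule misses a true 20-point difference in about two of three trials (100 − 33 = 67% to 100 − 30 = 70%).

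**What a trigger would cost Aim 1.** With 75 / 15 = 5 patients a month, those with a 3-month assessment number 5 × (month − 3): 15, 30 and 45 of 75 at months 6, 9 and 12. This holds only if stopping also ends follow-up, which the plan does not say.

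**The case for a change.** The strongest opposing case is that the sentence is written as a commitment, so an undefined trigger is a defect under any reading. On this view, wording costs nothing: name the endpoints, test and level, or say that the review is a judgement.

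Much of this stands. The rule is under-specified, the 4 v 0 example shows that the open choices can flip a decision, and an added sentence would do no harm. But it does not show that any stated figure or method is wrong. The candidate remedies are opposites, a formal boundary or an explicit judgement, and the argument does not favour either. The false-trigger figures run from 0.3% to 30% on assumed inputs alone. Most continuity-corrected single-endpoint cases stay at or below 5% even after five looks.

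The blinding point is also fair but limited. An aggregate table does not usually reveal a patient's arm. A 4 v 0 table would reveal it to a co-investigator who knows the infected patients, while a 3 v 1 table would not do so with certainty. The data-access statements do differ. DATA AND SPECIMEN MANAGEMENT includes the VAD nurse and the Research Coordinator, CONFIDENTIALITY limits access to IRB-approved investigators, and the privacy section names only the PI and co-investigators. RESOURCES AVAILABLE also gives the PI responsibility for analysis. Still, the Research Coordinator has access under the first statement, and the available text gives that role no checklist scoring. A route that keeps assessors away from by-arm tables therefore exists.

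How Aim 1 would be analysed after cross-over is not stated. It matters only if cross-over opens, and analysis by randomised arm is the usual default.

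**Conclusion.** No change to the plan follows. The review sentence lacks a complication list, test, level and multiplicity allowance, but it is a participant-protection statement in a small single-centre training trial, not an efficacy interim analysis. The primary checklist comparison is not tested at these reviews, so its type I error is not directly inflated.

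Read as an unadjusted 0.05 test of one complication, the rule carries a false-trigger chance of about 0.5% to 17% over five looks. This rests on 75 patients, 1:1 allocation, even accrual and assumed event rates of 5% to 40%. Read as clinical judgement, it has no such rate. Tightening the level trades false alarms for missed harm: at 0.016, about 5% false triggers and 30–33% detection, against 15% and 50–54% at 0.05. Leaning towards sensitivity is a fair choice for a safety review.

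The remaining gaps are ones that a sensible team fills in practice: weigh driveline infections and re-hospitalizations, use an exact or corrected test when counts are small, have a non-assessor prepare the tables, and analyse by randomised arm.

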The research settings for recruitment and enrollment of patients is Northwestern Memorial Hospital, Northwestern University, Chicago, IL. Patients will be recruited either at the medical center (while the patient is hospitalized) or during a clinic visit. The co-investigators, who provide care to patients with ventricular assist devices (VADs) will share information about the study with patients. If the patient's caregiver is not present at this time, we will contact them via phone or via mailed brochure to explain the study and then consent in person when they arrive for their VAD training.

The PI, CO-I or VAD nurse, will further explain the study to patients and caregivers, encourage them to ask questions, and obtain written informed consent. Patients and caregivers will be informed that if they decline to participate in the study, it will not prejudice current patient care, and they may discontinue participation at any time during the study with no adverse impact to their treatment or care. Verbal and written information provided to potential participants during informed consent will include the following: the purpose of the study, the nature of the questions asked during interviews, the method and frequency of skills assessment completion, the length of time required, the voluntary nature of participation in the study, the ability to not respond or participate in any parts if requested, the freedom to withdraw from the study at any time without consequences, the potential risks and benefits of study participation,

and the confidentiality of information gathered. A brochure with an overview of the study will also be provided. Patients will also be shown their study results, if desired. Patients who are enrolled in INTERMACS will also be informed that INTERMACS will securely transmit data to Northwestern, as well, which is already done for other studies. We will also incorporate language into their consent form that includes a statement about INTERMACS protected health information being transmitted securely to Northwestern. Patients who agree to participate in the study will sign an informed consent form. A copy of the signed consent form will be given to the patient, a second copy of the consent form will be placed in the patient's medical record, and the original copy will be kept and filed by the RC

NUMBER OF LOCAL PARTICIPANTS:

We expect to recruit 75 patients and 75 caregivers. One caregiver will be identified by each patient subject.

CONFIDENTIALITY:

Procedures are in place to ensure the confidentiality of identifying information in INTERMACS, the Enterprise Data Warehouse, and Northwestern University protected research servers. These procedures are described in detail below.

We will incorporate a section into the informed consent that authorizes the study investigators to share personal health and other information from this study with persons and/or entities identified on the form, according to the rules and regulations of the Health Insurance Portability and Accountability Act (HIPAA). These procedures will thus inform patients of authorized personnel with whom data will be shared in a secured fashion and contribute to the confidentiality of a subject's identifying information and its protection from unauthorized access.

INTERMACS currently follows Federal Information Security Management Act of 2002 (FISMA) guidelines using the National Institute of Standards and Technology (NIST) Special Publication (SP) 800-53 Rev 4 for the protection of federal data. This security guideline helps ensure that all data entered and processed within INTERMACS is protected using specific security controls for integration of information security and privacy into organizational processes including enterprise architecture. INTERMACS also uses HIPAA overlays in addition to FISMA requirements for the protection of sensitive information. In addition to federal requirements, all sensitive data is sent to its recipients via secure encrypted e-mail. The INTERMACS Data Coordinating Committee facility has limited access via the use of electronic locking mechanisms and tracking. Only authorized INTERMACS personnel (CO-I) will have access to INTERMACS data.

All data will be stored on the research assistants' or PI's computer that is encrypted and password protected. Each patient and caregiver will be assigned a unique ID used to identify them. All paper records, including checklists, surveys, consent forms, and manual chart review forms will be locked in the Research Assistant's office in a locked file cabinet. Only IRB approved investigators on this IRB protocol form will have access to collected data. All data will be destroyed one year after study publication.

PROVISIONS TO PROTECT THE PRIVACY INTERESTS OF PARTICIPANTS:

Individual's participation will be voluntary. Only the PI, and co-investigators will have access to the data. The information gathered will not effect the patient or their care in any way other than for educational research purposes to improved communication skills training. Each patient and caregiver will be assigned a unique ID used to identify them.

CONSENT PROCESS:

Patients

Patients who participate in our proposed research will provide informed consent. Patients will be recruited either at the medical center (while the patient is hospitalized), during a clinic visit, or via an opt-out letter and follow-up telephone call. The co-investigators who provide care to patients with ventricular assist devices (VADs) will share information about the study with patients.

The PI, CO-I or VC, will further explain the study to patients, encourage them to ask questions, and obtain written informed consent. Patients will be informed that there will be no penalty for not participating in this study. Verbal and written information provided to potential participants during informed consent will include the following: the purpose of the study, the method and frequency of skills assessment completion, the length of time required, the voluntary nature of participation in the study, the ability to not respond or participate in any parts if requested, the freedom to withdraw from the study at any time without consequences, the potential risks and benefits of study participation, and the confidentiality of information gathered. Patients who are enrolled in INTERMACS will also be informed that INTERMACS will securely transmit data to Northwestern, as well, which is already done for other studies. We will also incorporate language into the consent form that includes a statement about INTERMACS protected health information being transmitted securely to Northwestern. Patients who agree to participate in the study will sign an informed consent form. A copy of the signed consent form will be given to the patient, a second copy of the consent form will be placed in the patient's medical record, and the original copy will be kept and filed by the research coordinator.

Caregivers

Caregivers who participate in our proposed research will provide informed consent. They will be recruited either at the medical center (while the patient is hospitalized), during a clinic visit, or via an opt-out letter and follow-up telephone call. The co-investigators who provide care to patients with ventricular assist devices (VADs) will share information about the study with caregivers. If a patient wants to enroll in the study and their caregiver is not present at the time, we will contact them via phone to explain the study and then consent in person when they arrive for their VAD training.

The PI, CO-I or VC, will further explain the study to caregivers, encourage them to ask questions, and obtain written informed consent. Caregivers will be informed that there will be no penalty for not participating in this study. Verbal and written information provided to potential participants during informed consent will include the following: the purpose of the study, the method and frequency of skills assessment completion, the length of time required, the voluntary nature of participation in the study, the ability to not respond or participate in any parts if requested, the freedom to withdraw from the study at any time without consequences, the potential risks and benefits of study participation, and the confidentiality of information gathered. Caregivers who agree to participate in the study will sign an informed consent form. A copy of the signed consent form will be given to the caregiver, a second copy of the consent form will be placed in the patient's medical record, and the original copy will be kept and filed by the research coordinator.
